9.2 Test and Observation Items and Time Points

9.2.1 Subject characteristics

9.2.1.1 Medical History/Demographic Characteristics

The investigator (or subinvestigator) will identify the following subject demographic characteristics at screening (Days -30 to -2) and record the results in the CRF.

- (1) Sex
- (2) Race
- (3) Date of birth (in AD)
- (4) Height
- (5) Body weight
- (6) Medical history
- (7) History of allergy (including drug allergies)
- (8) Drinking status
- (9) Smoking status

9.2.1.2 Inclusion/exclusion criteria

The investigator (or subinvestigator) will confirm whether each subject meets the inclusion or exclusion criteria at screening and hospitalization and before the first administration, and record the results in the CRF.

9.2.1.3 Serological test

A serological test (HBs antigen, serological test for syphilis, HCV antibody, and HIV antigen/antibody) will be performed at screening. The investigator (or subinvestigator) will record the results in the CRF for fulfillment of the inclusion and exclusion criteria.

9.2.1.4 Drug and Alcohol Abuse Screening

At screening, the subjects will undergo the urine drug test (phencyclidines, benzodiazepines, cocaine narcotics, stimulants, hemp, morphine-based anesthesia, barbiturates, tricyclic antidepressants) and breath alcohol test. The investigator (or subinvestigator) will record the results in the CRF for fulfillment or not-fulfillment of the inclusion and exclusion criteria.

9.2.1.5 Height, weight, BMI

At the time points shown in the table below, the subjects' height and body weight will be measured to calculate their BMI. The investigator (or subinvestigator) will record the height and body weight in the CRF. The BMI on Day -1 (at hospitalization) will be calculated based on the height at screening and body weight on Day -1 (at hospitalization).

| Test schedule | Screening | Height, weight, BMI |
|---------------|---------------------------------------|---------------------|
| | Admission | Body weight, BMI |
| | End-of-study assessment or withdrawal | Body weight |

BMI formula:

 $BMI = Body weight (kg)/height (m)^2 (rounded to one decimal place)$

9.2.2 Concomitant medications

The investigator (or subinvestigator) will confirm whether each subject has used any medications (including commercially available drugs) other than the investigational product, between the start of investigational product administration and completion of the end-of-study assessment. If any, the investigator (or subinvestigator) will record the drug name, dose, unit, route, frequency, duration, and reason for administration in the CRF.

9.2.3 Administration status

The investigator (or subinvestigator) or study collaborator will record the date and time of the investigational product (edaravone oral suspension) administration in the CRF.

The investigator (or subinvestigator) or study collaborator will record the times of start and end of the investigational product (edaravone intravenous formulation) administration in the CRF. If the administration is interrupted or the entire dose cannot be administered, he/she will record the time of interruption and the remaining amount in the CRF.

9.2.4 Pharmacokinetic Assessments

Blood sampling will be performed for measurement of plasma concentrations of unchanged edaravone, sulfate conjugate, and glucuronide conjugate, and urine sampling will be performed for measurement of urine concentrations of them. The investigator (or subinvestigator) or study collaborator will record the dates and times of the blood and urine sampling and the sampled urine volume in the CRF. The measurement will be conducted in the drug concentration measurement site.

If any other assessments are scheduled at the same time point of blood sampling for plasma drug concentration measurement, blood sampling will be performed at the exact scheduled time point, and other assessments will be performed before or after the blood sampling. In principle, a 12-lead ECG and vital signs (except for body temperature) will be measured before the blood sampling for plasma drug concentration measurement and safety evaluation. After investigational product administration, the urine will be forced to void at 24-hour intervals.

The acceptable time range for the time of each blood or urine sampling (forced void) will be specified in a separate document.

9.2.4.1 Measurement of plasma concentrations of unchanged edaravone, sulfate conjugate, and glucuronide conjugate

- (1) Time points and volume of blood sampling
 - 1) Advance administration of Edaravone oral suspension group

(a) Time points of blood sampling

| Period I | Day 1 | Before administration of edaravone oral suspension, 0.083, 0.25, 0.5, 0.75, 1, 1.5, 2, 4, 6, 8, 10, and 12 hours after administration |
|----------|-------|---|
| | Day 2 | 24 and 36 hours after administration of edaravone oral suspension |
| | Day 3 | 48 hours after administration of edaravone oral suspension |

CONFIDENTIAL

| Period II | Day 4 | Before administration of edaravone intravenous |
|-----------|-------|---|
| | | formulation |
| | | 0.25, 0.5, 1, 1.083, 1.25, 1.5, 1.75, 2, 3, 4, 6, 8, and 12 |
| | | hours after administration |
| | Day 5 | 24 and 36 hours after administration of edaravone |
| | - | intravenous formulation |
| | Day 6 | 48 hours after administration of edaravone intravenous |
| | | formulation |

- (b) Frequency of blood sampling: 33
- (c) Volume of blood sampling: 5.5 mL, Total: 181.5 mL (per subject)

2) Advance administration of Edaravone intravenous formulation group

(a) Time points of blood sampling

| (a) In | ne poi | nts of bloc | od sampling |
|--------|--------|-------------|--|
| Perio | d I | Day 1 | Before administration of edaravone intravenous |
| | | · | formulation |
| | | | 0.25, 0.5, 1, 1.083, 1.25, 1.5, 1.75, 2, 3, 4, 6, 8, and 12 |
| | | | hours after administration |
| | | Day 2 | 24 and 36 hours after administration of edaravone |
| | | · | intravenous formulation |
| | | Day 3 | 48 hours after administration of edaravone intravenous |
| | | | formulation |
| Perio | d II | Day 4 | Before administration of edaravone oral suspension, |
| | | • | 0.083, 0.25, 0.5, 0.75, 1, 1.5, 2, 4, 6, 8, 10, and 12 hours |
| | ļ | | after administration |
| | | Day 5 | 24 and 36 hours after administration of edaravone oral |
| | | - | suspension |
| | | Day 6 | 48 hours after administration of edaravone oral suspension |
| | | | |

- (b) Frequency of blood sampling: 33
- (c) Volume of blood sampling: 5.5 mL, Total: 181.5 mL (per subject)

9.2.4.2 Measurement of urine concentrations of unchanged edaravone, sulfate conjugate, and glucuronide conjugate

Urine volume will be measured at voiding and the urine specimen will be processed (see Section 9.2.4.3). Urine will be forced to void before administration, 24 hours after administration, and 48 hours after administration.

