#### 7.1.3.2. Pharmacokinetic Parameters

(1) Below the limit of quantification

For the calculation of PK parameters, actual sampling time (in hours rounded to 3 DPs) relative to dosing should be used. Concentration below the limit of quantification (BLQ) will be imputed with a value of 0. For calculation of AUCs, missing data will be treated as if the respective sample never had been scheduled for the calculation by the linear-linear trapezoidal

rule. For Ae, Ae% and CLR, geometric mean and geometric CV% will be calculated only when all the individual Ae, Ae% and CLR is greater than 0 in each sampling time point.

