### (2) PK related

The allowable time window will be the following.

After administration of Edaravone oral suspension

Nominal Time Point	Window
Predose	Within 60 min before dosing
0.083 h after dosing	Nominal time point ± 1 min
0.25, 0.5, 0.75, 1, 1.5, 2, 4, 6, 8, 10, 12 h after dosing	Nominal time point ± 5 min
24, 36, 48 h after dosing	Nominal time point ± 15 min

After administration of Edaravone intravenous formulation

Nominal Time Point	Window
Predose	Within 60 min before dosing
0.25, 0.5 h after dosing	Nominal time point ± 5 min
1 h after dosing	End time of dosing + 0-1 min
1.083 h after dosing	End time of dosing + 4-6 min
1.25 h after dosing	End time of dosing + 10-20 min
1.5, 1.75, 2, 3, 4, 6, 8, 10, 12 h after dosing	Nominal time point ± 5 min
24, 36, 48 h after dosing	Nominal time point ± 15 min

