### **8.4.2. Analysis of Primary Endpoints**

The parameters  $AUC_{0-t}$ ,  $AUC_{0-\infty}$  and  $C_{max}$  of unchanged edaravone will be log transformed prior to statistical analysis. The analysis will be by analysis of variance (ANOVA) taking account of formulation (oral suspension or intravenous formulation). Factors accounting for the following sources of variation: sequence, subjects nested in sequences, period, and treatment. Estimates of mean difference between formulations (oral suspension minus intravenous formulation) on the log scale and 90% CI for the difference (based on the residual mean square in the ANOVA) will be back transformed to present means and 90% CI for the ratio of oral suspension to intravenous formulation.

90% CI for the ratio of  $AUC_{0-t}$ ,  $AUC_{0-\infty}$  and  $C_{max}$  of unchanged edaravone which lie entirely within the limits of 0.8000 to 1.2500 provides bioequivalence between intravenous formulation and oral suspension. As reference, the same analysis will also be on  $AUC_{0-t}$ ,  $AUC_{0-\infty}$  and  $C_{max}$  of sulfate conjugate and glucuronide conjugate and other reference pharmacokinetic parameters of unchanged edaravone, sulfate conjugate, and glucuronide conjugate, such as  $t_{max}$ ,  $AUC_{0-all}$ ,  $MRT_{0-\infty}$ , and  $Kel$ .  $T_{max}$  will not be log transformed prior to statistical analysis.

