## Appendix 1 Pharmacokinetic Parameter Calculations

- Actual blood sampling times will be used in the calculation of pharmacokinetic parameters
- All concentrations below the LLOQ will be set at zero for pharmacokinetic calculations
- When Kel is missing (or cannot be determined),  $t_{1/2}$ ,  $AUC_{0-\infty}$ ,  $AUC\%_{ex}$ , CL/F, MRT,  $V_z/F$  and  $V_{ss}/F$  will not be calculated.

PK Parameter Calculations		
Parameters	Unit	Calculation
$C_{max}$	ng/mL	will be determined by visual inspection
$AUC_{0-\infty}$	ng·h/mL	$AUC_{0-\infty} = AUC_{0-t} + C_{last} / Kel$ $C_{last}$ : last measurable concentration
$AUC\%_{ex}$	%	$AUC\%_{ex} = (AUC_{0-\infty} - AUC_{0-t}) / AUC_{0-\infty} \times 100$
$AUC_{0-t}$	ng·h/mL	will be calculated using the linear trapezoidal method and actual times $AUC_{0-t} = \sum_{i=1}^n \frac{t_i - t_{i-1}}{2} (C_{i-1} + C_i)$
$AUC_{0-24}$	ng·h/mL	will be calculated using time until 24 h drug concentration
$AUC_{0-all}$	ng·h/mL	will be calculated using time until the last sampling time point
$t_{max}$	h	Measured time of $C_{max}$
$t_{1/2}$	h	$t_{1/2}$ will be determined as: $t_{1/2} = \log_e(2) / Kel$
Kel	/h	
The exponential rate constant of the terminal phase, Kel, will be estimated by log-linear regression, if determinable. The number of data points included in the regression will be determined by visual inspection. Wherever possible, a minimum of 3 data points will be used in the estimation of Kel.
 
During the analysis, this calculation method repeats regressions using the last three points with non-zero concentrations, then the last four points, last five, etc. The time of maximum concentration (<math>t_{max}</math>) will be excluded from the estimation of Kel.
 
Points with a value of zero for the dependent variable are excluded. For each regression, an adjusted <math>R^2</math> is computed
 $Adjusted R^2 = 1 - \frac{(1 - R^2) \times (n - 1)}{(n - 2)}$ 
where n is the number of data points in the regression and <math>R^2</math> is the square of the correlation coefficient.

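### Oral dosing has no 3 h plasma sample but IV dosing does; with linear-trapezoid AUC this probably biases the confirmatory oral/IV AUC ratio upward, by about 2% under assumed profiles

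*Protocol*

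**What the plan says.** Protocol 9.2.4.1 sets a different plasma schedule for each formulation, and each formulation keeps its schedule in both sequences.

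- Oral, Day 1 or Day 4: pre-dose and "0.083, 0.25, 0.5, 0.75, 1, 1.5, 2, 4, 6, 8, 10, and 12 hours after administration".
- IV, Day 1 or Day 4: pre-dose and "0.25, 0.5, 1, 1.083, 1.25, 1.5, 1.75, 2, 3, 4, 6, 8, and 12" hours.
- Both: 24, 36 and 48 h.

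The protocol gives the total as "Frequency of blood sampling: 33". The oral list has 16 samples and the IV list 17, and 16 + 17 = 33, so the missing 3 h oral point is not a text-extraction fault. The oral window row in SAP 7.2 (2) agrees: "0.25, 0.5, 0.75, 1, 1.5, 2, 4, 6, 8, 10, 12 h after dosing". The IV row in the same section reads "1.5, 1.75, 2, 3, 4, 6, 8, 10, 12 h after dosing", which includes a 10 h time that the protocol's IV schedule lacks.

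SAP Appendix 1 says that AUC0-t "will be calculated using the linear trapezoidal method and actual times", and SAP 7.1.3.2 also names the linear rule. Neither gives a logarithmic rule for the falling limb. AUC0-∞ is AUC0-t plus C_last/Kel. Under SAP 8.4.2, the 90% CIs for the oral/IV ratios of AUC0-t, AUC0-∞ and Cmax must all lie within 0.8000 to 1.2500.

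Protocol 9.2.4.3 says that sampling times were based on three earlier studies. It does not explain why the grids differ around 3 h.

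**The concern.** By 2 h both profiles should be falling. Protocol section 1 (3) puts suspension tmax at 0.4 to 0.8 h, and the infusion ends at 1 h. From there the oral grid runs 2, 4, 6, 8, 10, 12 h and the IV grid 2, 3, 4, 6, 8, 12 h. Oral has its extra point late, where little area is left, and lacks one where the decline is probably still fast.

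A straight line lies above a convex curve, so the linear rule overstates area on such a decline. One 2 h step overstates it more than two 1 h steps. The larger error falls in the numerator of a ratio that decides bioequivalence. It is systematic, so more subjects would only narrow the interval around a shifted estimate. Because AUC0-∞ is built on AUC0-t, both confirmatory AUCs carry it.

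**Working it through.** **1. The plan's own sample size.** Inputs from protocol 6.1: SD 0.232 for AUC0-∞, ratio 1.06, two one-sided 5% tests, power at least 90%, N = 36. I used a two-period crossover on the log scale with SE = SD × √(2/N) and N − 2 degrees of freedom, integrating over the residual variance. Power is 0.889 at N = 34 and 0.90 at N = 36, so the stated 36 reproduces with almost no margin.

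**2. Effect of the missing sample.** Write C2, C3, C4 for the concentrations at 2, 3 and 4 h.

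- One step: C2 + C4.
- Two steps: (C2 + 2·C3 + C4)/2.
- Difference: (C2 + C4 − 2·C3)/2, which is positive for any convex decline.

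For a local half-life h, let k = ln 2/h and C2 = 1. The true area is (1 − e^(−2k))/k. At h = 1 h the true area is 1.082, one step gives 1.250 (+15.5%) and two steps give 1.125 (+4.0%). The difference of 0.125 is 11.6% of the segment. If the segment holds 10% of AUC (an assumption), the missing sample adds this to oral AUC:

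| Local half-life (h) | Added to AUC |
|---|---|
| 2 | 0.3% |
| 1 | 1.2% |
| 0.75 | 2.0% |
| 0.5 | 4.2% |

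The answer depends on a decline rate and an AUC share that the documents do not give.

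**3. Range under assumed profiles.** From protocol 6.1: IV AUC 1738 and Cmax 1195, oral AUC 1828 and Cmax 1661. From protocol section 1 (3): suspension tmax 0.4 to 0.8 h, three-phase elimination, terminal half-life 5.1 to 11.8 h. Assumed: fast-phase half-life 0.05 to 0.5 h, middle-phase half-life 0.5 to 2.5 h, terminal phase 2 to 25% of AUC, mixed zero- and first-order absorption. Each profile was integrated on the planned grids and compared with its fine-grid AUC.

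In the 6060 profiles with oral Cmax within 5% and IV Cmax within 3% of the planning values:

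| Quantity | Median | 5th to 95th percentile |
|---|---|---|
| 2-4 h excess, oral (% of AUC) | 2.7% | 0.8 to 4.5% |
| 2-4 h excess, IV (% of AUC) | 1.1% | 0.2 to 1.7% |
| Effect of no oral 3 h sample | 1.9% | 0.5 to 3.2% |
| Net bias in oral/IV ratio | +2.0% | +0.5 to +3.6% |
| Net bias with an oral 3 h sample added | about 0% | −1.0 to +1.9% |

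Other sets vary the answer:

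- A second three-phase set (IV Cmax within 5%, oral within 10%): median +2.0%, range −0.4 to +3.7%. The median falls to about 0% with either the 10 h-to-3 h swap or linear-up/log-down integration.
- Looser matching (oral Cmax within 25%, IV within 10%): 0.4 to 4.1%, median 2.5%, with 2.6% of profiles negative.
- Simple first-order absorption with tmax near 0.3 h: 0.7 to 1.6%.

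The absent IV 10 h sample adds only about 0.1% to IV AUC.

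**4. Consequence for the AUC test.** SD 0.232, with the bias multiplying the true ratio:

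| Bias | Power at 1.06, n=36 | Power at 1.06, n=42 | False equivalence at 0.80, n=42 |
|---|---|---|---|
| 0 | 0.90 | 0.94 | 5.0% |
| +1% | 0.87 | 0.91 | 7.3% |
| +2% | 0.83 | 0.88 | 10.4% |
| +3.5% | 0.76 | 0.81 | 16.4% |

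At a true ratio of 1.25 with n=42, +2% makes the test conservative: the error rate falls from 5% to 2.1%.

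**The case against.** A reader might infer four stronger things, none of which the documents support.

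- That only oral AUC is over-integrated. The linear rule overstates the IV 2-4 h segment too, by roughly 40% of the oral error. Only the difference reaches the ratio.
- That the inflation is established at 2 to 5%. No 2-4 h concentration, distribution half-life or partial AUC is stated. In the closest-matched profiles 2% is the centre, not the floor, and 5% lies beyond the 95th percentile.
- That the ratio always rises. The 2-4 h effect is positive for a convex decline, but errors elsewhere on the grids can offset it, and a few profiles give a net bias at or below zero.
- That this error would decide the trial. All three parameters must pass. At the planned Cmax ratio of 1.40, the chance that Cmax meets both limits is about 0.2% or less at n = 36 to 42. On the plan's own assumptions, Cmax is the obstacle.

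The power loss may also be overstated. Forty-two subjects are planned, and SAP 6.3 records none excluded from PK analysis. The planned 1.06 is rounded up from 1828/1738 = 1.052; at that ratio with n=42 and +2%, power is still 0.907. The 1.06 may already contain similar error, since the earlier studies' sampling times and AUC rules are not given. Route-specific grids are reasonable near the peak, where the two inputs differ.

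These points lower the impact. They do not explain different grids once both profiles are falling, and they do not remove the bias. The extra IV 10 h window is a wording mismatch and is not evidence of bias.

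**Conclusion.** The point stands as a probable, modest upward bias in the confirmatory AUC ratio. The sampling asymmetry and the linear rule are facts of the plan. The size is not: about 0 to 3.5%, centred near +2%, rests on assumed three-phase profiles matched to the planning figures. The power figures further assume that the bias adds to 1.06 and that 0.232 is a log-scale SD; read as a CV it gives 0.911 falling to 0.839 at n=36, much the same. The false-equivalence figure concerns AUC alone, at a true ratio far from the planned one. Whether the bias helps or hurts an equivalence claim depends on the true ratio; at 1.06 it moves the estimate toward the upper limit. It merits correction because it is systematic, affects a confirmatory endpoint and is cheap to check.

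**What to change.** **If sampling is still open:** replace the oral 10 h sample with a 3 h sample in protocol 9.2.4.1, the schedule tables and the oral windows of SAP 7.2. The total stays at 33 samples and 181.5 mL per subject. The cost is one fewer oral point between 8 and 12 h for estimating Kel; 8, 12, 24, 36 and 48 h remain.

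**If sampling is complete,** as the data review reported in SAP 6.3 indicates: specify in SAP 8.4.2 and Appendix 1 a linear-up/log-down calculation of AUC0-t and AUC0-∞ for both formulations, at least as a stated sensitivity analysis of the bioequivalence conclusion. Record it with its reason as protocol 13.5 requires, and update SAP section 10, which now reports no changes. This uses existing concentrations and costs one extra run. Repeating the linear analysis without the IV 3 h sample would be a useful further check.

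**Separately:** reconcile the 10 h IV window in SAP 7.2 with the protocol's IV schedule, which has no 10 h sample.

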9.2.4.3 Processing and storage of specimens

(1) Specimens for measurement of plasma concentrations of unchanged edaravone, sulfate conjugate, and glucuronide conjugate

Promptly after drawing roughly 5.5 mL of blood from the vein into a vacuum tube with heparin sodium, gently invert the tube several times. The subsequent procedures should be performed at ice temperature and completed within 120 minutes after the blood sampling.

Transfer the blood into tubes with a stabilizer that has been supplied by the

CONFIDENTIAL

sponsor, and centrifuge the tubes at 4°C, 1,500 g for 10 minutes, so as to complete the centrifugation within 30 minutes after blood sampling. Accurately place the specified amount of plasma into tubes (the primary specimens and backup specimens) with the fixed amount of internal standard, stabilizer, and buffer that has been supplied by the sponsor, and store them at \leq -70°C. Additional details regarding the procedure are provided in a separate procedure.

Pack the primary specimen and send it in a frozen state with a sufficient amount of dry ice to the sponsor, send the backup specimens, as well.

(2) Specimens for measurement of urine concentrations of unchanged edaravone, sulfate conjugate, and glucuronide conjugate

Collect voluntary urine and measure its volume. Accurately put the specified amount of the urine into test tubes (the primary specimens and backup specimens) containing the fixed amount of stabilizer provided by the sponsor, and store them at -70°C or below. Additional details are specified in a separate procedure.

Pack the primary specimen and send it in a frozen state with a sufficient amount of dry ice to At the request of the sponsor, send the backup specimens, as well.

[The above specimens (1) and (2) will be sent to

[Rationales for setting]

Timings of blood sampling were set on the basis of the results of the phase I clinical pharmacology studies (MT-1186-J01, MT-1186-J02, and MCI-186-J25 studies) and in consideration of "Clinical Pharmacokinetic Studies of Pharmaceuticals" (PFSB/ELD Notification No. 796 dated June 1, 2001) [3], the "Guideline for Bioequivalence Studies of Generic Products" (PFSB/ELD Notification No. 0229-10 dated February 29, 2012) [1], and the Guidance for Industry: Bioavailability and Bioequivalence Studies Submitted in NDAs or INDs-General Considerations (March 2014) [2].

9.2.5 Safety Assessments

The safety assessment period will be between the start of investigational product administration and the completion of the end-of-study assessment.

9.2.5.1 Objective findings

The investigator (or subinvestigator) will check for results of all of the following tests without delay.

(1) General laboratory tests

The following test items will be measured. The approximate blood volume per sampling is 2 mL for the following 1), 6 mL for 2), 1.8 mL for 3), and 6 mL for 5), described below. The investigator (or subinvestigator) or study collaborator will record the measurement results in the CRF.

1) Hematology:

CONFIDENTIAL

Hemoglobin, hematocrit, red blood cell count, white blood cell count, platelet count, MCH, MCHC, MCV, differential white blood count

2) Biochemistry:

Na, K, Cl, Ca, inorganic phosphorus, urea nitrogen, creatinine, uric acid, total bilirubin, direct bilirubin, ALT, AST, γ-GTP, ALP, LDH, CK, amylase, total cholesterol, triglycerides, LDL-C, HDL-C, total protein, albumin, glucose

3) Coagulation test:

Prothrombin time, activated partial thromboplastin time

4) Urinalysis:

Sediment, qualitative tests (pH, specific gravity, protein, glucose, occult blood, urobilinogen, bilirubin, ketones), and

hCG (performed only for female subjects at screening, on Day -1, and at the end-of-study assessment)

5) Other (serological test):

HBs antigen, serological test for syphilis, HCV antibody, HIV antigen/antibody (only at screening)

6) Other (drug/alcohol abuse screening):

Urine drug abuse screening (phencyclidines, benzodiazepines, cocaine narcotics, stimulants, hemp, morphine-based anesthesia, barbiturates, tricyclic antidepressants) and breath alcohol test (only at screening)

(a) Test schedule:

To be performed in the fasting state at the following time point (before breakfast).

| Screening | | No specifications |
|-------------------------|------------------|---|
| Hospitaliza | ation (Day -1) | No specifications |
| Period I | Day 3 | 48 hours after investigational product administration |
| Period II | Day 6 | 48 hours after investigational product administration |
| End-of-stu withdrawa | dy assessment or | No specifications |

- (b) Frequency of blood sampling: 5
- (c) Total volume of blood sampling: 55 mL (per subject) (For details, see "9.3 Volume of blood sampling")

(2) Vital signs (blood pressure, pulse rate, body temperature)

Systolic and diastolic blood pressure, pulse rate, and axillary body temperature (in Celsius; rounded to one decimal place) of each subject will be measured at the time points shown in the table below. The investigator (or subinvestigator) or study collaborator will record the date, time, and results of the measurement in the CRF. The measurement will be performed in the subject's fasting state (before breakfast).

Systolic and diastolic blood pressure will be measured after at least a 5-minute rest in a lying position. One measurement will be taken for each time point. The measurements will be taken in the same arm throughout the study period, in principle.

CONFIDENTIAL

If blood sampling and a 12-lead ECG or vital sign (except for body temperature) measurement are scheduled at the same time point, blood will be drawn after the 12-lead ECG or vital sign (except for body temperature) measurement.

Test schedule

| Screening | | No specifications |
|----------------------------|-------------------|--|
| Hospitaliza | tion (Day -1) | No specifications |
| Period I | Day 1 | Before and 1 hour after investigational product administration |
| | Day 2 | 24 hours after investigational product administration |
| | Day 3 | 48 hours after investigational product administration |
| Period II | Day 4 | Before and 1 hour after investigational product administration |
| | Day 5 | 24 hours after investigational product administration |
| | Day 6 | 48 hours after investigational product administration |
| End-of-stud or withdray | dy assessment val | No specifications |

(3) 12-lead ECG

After at least a 5-minute rest in a lying position, a 12-lead ECG will be recorded at the time points shown in the table below. The investigator (or subinvestigator) will record the date and time of measurement, heart rate, QTcF, PR interval, QT interval, RR interval, QRS interval, and findings in the CRF. The measurement will be performed in the subject's fasting state (before breakfast).

If blood sampling and a 12-lead ECG or vital sign (except for body temperature) measurement are scheduled at the same time point, blood will be drawn after the 12-lead ECG or vital sign (except for body temperature) measurement.

Test schedule

| Screening | | No specifications |
|----------------|-------------|--|
| Hospitalizatio | on (Day -1) | No specifications |
| Period I | Day 1 | Before and 1 hour after investigational product administration |
| | Day 2 | 24 hours after investigational product administration |
| | Day 3 | 48 hours after investigational product administration |
| Period II | Day 4 | Before and 1 hour after investigational product administration |

CONFIDENTIAL

| | Day 5 | 24 hours after investigational product administration |
|----------------------------------|-----------|---|
| | Day 6 | 48 hours after investigational product administration |
| End-of-study as or withdrawal | ssessment | No specifications |

